## 5.7 Withdrawal of Subjects

We will explain to the patients that they are not obligated to participate in the study. Additionally, we will explain to them that should they choose to become a study participant, they can withdraw any time after enrollment. Furthermore, we will explain to the patients that if they decline to participate in the study, their medical care will not be impacted, and they will receive the same medical care as planned before.

Should the enrolled subject damage, lose or have a malfunctioning study phone, a replacement will be provided to them at no expense. Such circumstances will not affect study participation nor incur any financial responsibility. However, if the subject has a pattern of losing the equipment generally it (phone /sensor) prevents acquisition of data and the study team may withdraw the subject.

## 6.0 Reporting

## Medical/Treatment History

Medical and treatment history data will be captured in the electronic case report system, to ensure that the subject meets all of the inclusion/exclusion criteria, specifically inclusion criterion number.

## Medications

Subject's current medications will be captured in the electronic case report system. Start dates if available will be noted. During the course of the study if a medication is stopped, stop dates will also be noted.

## Status and Event Questionnaire

The questionnaire will be read to the subject by a member of the study team during the clinic visit or telephone call, and answers will be recorded in the electronic case report system. The questionnaire identifies medical events that the subject can recall and report for the interval since the last inquiry, including events that occur at health care facilities outside the clinical setting of the investigator's site and which may otherwise be unknown to the site clinical staff. Events may include acute care utilization or adverse events, in which case AE/SAE evaluations are triggered.

## Adverse Event and Serious Adverse Event

Interim analyses. Two interim analyses will be performed, once 50 subjects and 100 subjects complete the study. The main goal of the interim analyses will be monitoring of patient safety. The anticipated possible adverse events fall into two categories: adverse events related to the study sensor and adverse events related to heart failure therapy.

Interim analysis of adverse events related to the study sensor. We will report to the DSMB the rate of AEs related to the study sensor. We anticipate these may include local allergic reaction to the adhesive, skin rash or skin abrasion. While not reported previously, systemic allergic reaction to the adhesive could also occur.

Interim analysis of adverse events related to heart failure therapy. The study intervention is expected to improve clinical outcomes in subjects with heart failure. However, since the algorithmic response triggered by a study alert calls for changes in heart failure therapy or changes in follow-up, there could be adverse events related to these changes triggered by study procedures.

The following events will be recorded, adjudicated and reported to the data coordinating center: - Over diuresis

- Hypotension induced by heart failure medications
- Other adverse events attributed to HF therapy
- Hospitalization

Reporting of interim analyses. The data coordinating center will tabulate the rates of adverse events at the time of the interim analyses.

Adverse events related to the study sensor will be presented for all study subjects, since all study subjects will wear the sensor regardless of randomization assignment. Adverse events related to

heart failure therapy will be tabulated by randomization assignment. This information will be generated by the data coordinating center and provided to the DSMB. The detailed data by randomization group will not be shared with study investigators unless a protocol modification is deemed necessary by the DSMB.

An Adverse Event is any undesirable experience (as judged by the principal investigator) associated with the use of a medical product in a subject that is not judged to be serious. The event will be deemed a Serious Adverse Event and should be reported to the IRB as such when the subject outcome is: Death, Life-threatening, Hospitalization (initial or prolonged), Disability or Permanent Damage, Required Intervention to Prevent Permanent Impairment, or other serious events as judged by the principal investigator. (See for reference FDA definition at:

<http://www.fda.gov/Safety/MedWatch/HowToReport/ucm053087.htm>)

All events shall be reported as per institutional guidelines.

Medical record request to non-VA hospital or emergency department or clinic

In the event that an acute care episode (a primary event) occurs at a non-VA facility, medical records will likely be provided to the clinical team. In the unlikely situation that this does not take place, the subject will be asked to sign a medical record release form, and the study team will obtain the records in question. Relevant data will be entered into the electronic case report system. A subject may also sign the medical record release at the time of consent to cover any possible outside admissions during enrollment.

Determination of Exacerbation timing/Cause

In the event that an acute care episode (a primary event) occurs and is determined to be an exacerbation of a subject's chronic conditions, the site PI will make a determination of the timing and cause of the exacerbation.

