Remote monitoring will start at the time of hospital discharge and continue for 90 days. The adhesive sensor patch will be attached to the subject's chest and paired with a smartphone. Continuous data will be uploaded automatically to a secure server for analytical platform processing. While all enrolled study subjects will receive the remote monitoring device, the subjects will be randomized in a 1:1 ratio to intervention vs. control arm. In the intervention arm, once physiological derangements correlated with impending HF exacerbation are identified by the analytical platform, a clinical alert will be generated and messaged to the electronic medical record (EMR). This alert will be visible to the local team providing heart failure care for the corresponding subject. If applicable, another convenient means of a backup notification to be defined in the implementation process may also be generated. Each site will have designated heart failure clinicians that will respond to the alerts. To reduce variation in response to clinical alerts, clinicians at the study sites will follow a standardized response algorithm. Based on the remote monitoring data, clinical symptoms and blood pressure the HF nurse will determine the suggested clinical action - medication up-titration, clinic visit or emergency room (ER) visit, and confirm with the physician that this action should be implemented. In the control arm, information from the sensor will be collected, but clinical alerts will not be generated or communicated to the providers.

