Should the subject damage, lose or have a malfunctioning study phone, a replacement will be provided to them at no expense. Such circumstances will not affect study participation nor incur any financial responsibility. However, if the subject has a pattern of losing the equipment generally it (phone /band aid) prevents acquisition of data and the study team may withdraw the subject.

After discharge from the hospital, the study staff will interact with the subject during follow-up visits scheduled for routine HF follow-up. Per clinical practice, the first clinic visit will be scheduled within 2 weeks of discharge. Subsequent study visits in the 90-day study period are expected to take place at day 30 and day 90 (+/- 7 days). If a face-to-face visit is not possible after a clinic visit the information will be obtained by calling the patient within the study visit window to address any study related questions, including device and phone functioning.

Additional encounters with providers will occur if alerts are generated based on remote monitoring data. The alert notification will be through the electronic health record (CPRS), and documentation of the response to the alert by the clinical team will also take place in CPRS. To reduce variation in response to clinical alerts, clinicians will follow a standardized response algorithm (**Figure 1**). Based on the remote monitoring data, clinical symptoms and blood pressure, the HF nurse will determine the suggested clinical action - medication up-titration, clinic visit, emergency room (ER) visit, or increase monitoring and confirm with the physician that this action should be implemented. In the control arm, information from the sensor will be collected, but clinical alerts will not be generated or communicated to the providers. Any treatment decisions will be made by the participant's clinical care team; the device only provides the alert and does not guide treatment. The research team will not be responding to the alarms. Of note, the remote monitoring data are not used for immediate decisions unrelated to the aims of the study. E.g., the device is not being used as an arrhythmia monitor and there is no real-time monitoring or clinician driven decision-making related to possible arrhythmias. In patients enrolled in the control arm, remote monitoring data are not being used for any clinical decisions. Patients are instructed to continue to seek care for their medical needs in the standard manner.

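### Apart from hospitalization, the by-arm interim safety table counts over-treatment events only when they are judged due to HF therapy, and that judgement can depend on arm

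*Combined protocol and SAP*

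**What the plan says.** Section 6.0, under Adverse Event and Serious Adverse Event, plans interim analyses when 50 and 100 subjects have completed, with safety as the main goal. It gives the reason for looking at HF-therapy events: "there could be adverse events related to these changes triggered by study procedures".

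It then states: "The following events will be recorded, adjudicated and reported to the data coordinating center". The list has four items: over diuresis, "Hypotension induced by heart failure medications", "Other adverse events attributed to HF therapy", and hospitalization. Adverse events related to "heart failure therapy will be tabulated by randomization assignment"; sensor events are shown for all subjects together. No adjudicator, criteria or masking is given. The same section defines an adverse event as "any undesirable experience (as judged by the principal investigator) associated with the use of a medical product".

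The Abstract says of an intervention-arm alert: "This alert will be visible to the local team providing heart failure care for the corresponding subject". Section 5.0, Experimental Procedures, adds: "Additional encounters with providers will occur if alerts are generated based on remote monitoring data". The team's response to an alert is documented in CPRS, and no alerts are generated in the control arm.

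**The concern.** The risk paragraph in section 5.2 names hypotension and dehydration as possible harms of the active arm. These are the harms that the interim table should show, and two of its four items admit an event only after someone decides that HF therapy caused it. Over diuresis carries no explicit attribution wording, but it is itself a causal label and sits under the HF-therapy heading.

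The person deciding may see in the chart that an alert and a therapy change came shortly before the event. That could raise attribution in the intervention arm, because a recent change is an obvious cause. It could also lower it, if low blood pressure after an alert is read as the deterioration that the alert predicted. Either way the numerator depends on a judgement that may depend on arm. Adjudicating events that have already been selected by attribution cannot restore those left out. Because the adverse event definition itself asks for an association with a medical product, unattributed events may not be recorded as adverse events at all.

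At stake is whether the DSMB can tell from the planned table if alert-driven changes in therapy harm patients who are not admitted.

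**Working it through.** **Plan's own figure.** There is none to reproduce. The documents give no adverse event rate, safety threshold or safety power; the precision figures in section 5.6 concern alerts and device function.

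**Inputs from the documents.** Randomization is 1:1 (Abstract). Looks at 50 and 100 completers (section 6.0) give about 25 and 50 subjects per arm.

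**Inputs that are assumptions.** True event risks, and the capture probability in each arm, meaning the chance that an event is found and attributed and so enters the table.

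**Formula.** Observed risk = true risk × capture. Hence observed risk ratio = true risk ratio × (capture in intervention ÷ capture in control).

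**Illustration 1: no true difference, risk 10% in both arms, all events found, attribution differs.**
- Attribution 80% v 40%: 0.10 × 0.80 = 8% against 0.10 × 0.40 = 4%; ratio 2.0. At 50 per arm: 50 × 0.08 = 4 against 50 × 0.04 = 2 expected events. Fisher's exact test on 4/50 v 2/50 gives two-sided p = 0.68. Over all possible tables, the chance of p ≤ 0.05 towards harm is about 4%.
- Attribution 60% v 50%: 6% against 5%; ratio 1.2. The chance of p ≤ 0.05 towards harm is about 1%.

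**Illustration 2: true control risk 15%, 50 per arm, exact binomial enumeration.** The last two columns give the chance of each result in the direction of harm.

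| True risk, intervention v control | Capture, intervention v control | Observed risk ratio | At least twice as many intervention events | Fisher p ≤ 0.05 |
|---|---|---|---|---|
| 15% v 15% | 0.8 v 0.8 | 1.0 | 14% | 1% |
| 15% v 15% | 0.9 v 0.6 | 1.5 | 37% | 5% |
| 15% v 15% | 0.9 v 0.45 | 2.0 | 56% | 10% |
| 30% v 15% | 1 v 1 | 2.0 | 54% | 35% |
| 30% v 15% | 0.6 v 0.9 | 1.33 | 24% | 5% |
| 30% v 15% | 0.45 v 0.9 | 1.0 | 12% | 1% |

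Unequal capture can thus create an apparent excess where there is none, or cancel a true doubling. Counts this small rarely reach nominal significance either way, so the effect is on the pattern that the DSMB sees rather than on a formal test.

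These runs apply one capture probability to a whole arm. An alert reveals the arm only for subjects who alert, and the absence of an alert does not prove control. The contrast between arms is diluted accordingly, by an amount that depends on the alert proportion, which the study is designed to estimate.

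**The case against.** The case on the other side has real force.

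- **Controls can have these events.** A reader might infer from the words about changes triggered by study procedures that controls cannot contribute. The documents do not support that: the sentence is rationale, the list refers to HF medications and HF therapy, which controls can also receive, and the table is by assigned arm.
- **Controls are not seen only at scheduled visits.** That too might be inferred, and it is wrong. Section 5.0 tells patients to keep seeking care in the standard manner and reviews the record for emergency visits, unplanned outpatient visits and medication changes. The Status and Event Questionnaire asks about interval events, including those at outside facilities. None of this is specific to one arm. What stands is narrower: alerts add encounters, with blood pressure among the inputs to the response, so mild events may be found more often in the intervention arm.
- **Serious harm is largely covered.** Hospitalization is listed without an attribution condition, and death and life-threatening events are serious by outcome. The exposed part is hypotension and volume depletion without admission.
- **There is adjudication, and the DSMB can request data** (Data Monitoring). Masked adjudication would reduce the bias, but masking is not stated. A possible request is not a planned table, and it can recover only what was recorded.
- **Proportion.** For a 240-subject feasibility study, tabulating treatment-related events by arm is a defensible choice, and no stopping threshold is tied to the table. That limits the consequence, but safety is still the stated main purpose of both looks.

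**Conclusion.** The point holds within limits. For hypotension and volume depletion that do not lead to admission, the planned by-arm comparison rests on attribution that may be made with knowledge of the arm, and partly on arm-dependent detection. It can be distorted in either direction. The documents do not allow the size to be determined: every event risk and capture probability above is an assumption, and the example of 8% v 4% would not be statistically significant by itself.

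A reader might go further and conclude that the DSMB will be misled, or that a protocol modification would be wrongly prompted or suppressed. The documents do not support that, since they give no rates, no threshold and no decision rule. The change is nonetheless worth making, because it is cheap and removes the attribution part of the problem.

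**What to change.** In section 6.0, under the interim reporting text:

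1. Make the main safety comparison a by-arm table of all recorded hypotension and volume-depletion events, deaths and hospitalizations in all randomized subjects, regardless of attribution. Define these events so that they are recorded whether or not a cause is assigned.
2. Keep attribution to HF therapy as a second column, assigned without knowledge of arm where feasible, and state who adjudicates.
3. Record how each event was found (alert-driven encounter, scheduled visit or call, record review, usual care) and show counts by source descriptively. Do not use a table that drops events found at alert-driven encounters as evidence of safety: it removes events from the intervention arm only, where alert-driven harm would surface.
4. Include renal events only as clinically recorded, with the caveat that testing may differ by arm; the plan describes no common laboratory schedule.

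**Cost.** Revised interim table wording, event definitions, and a small amount of added event recording and eCRF work. The table will carry more background events. Arm-dependent detection remains, though it becomes visible. Treatment, visits and sample size are unchanged.

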### 3.0 Objectives

**STUDY AIMS** Aim 1. Implement remote monitoring into the clinical workflow of HF care.

Aim 1a. Design implementation strategies for non-invasive remote monitoring and algorithmic response to clinical alerts generated by the predictive analytics platform. In HF programs at five VA medical centers, eligible patients will be invited to enroll at the time of hospital discharge for HF exacerbation and receive a wearable monitor and a smartphone with cellular service for a 90 day period. We plan to enroll and randomize 240 subjects. Data continuously uploaded to a secure server will be analyzed by the predictive analytics algorithm and a clinical alert will be generated when physiological derangements correlated with impending HF exacerbation are identified. A clinical response algorithm will provide instructions for management response to the alert, to include medication changes and/or urgent/non-urgent outpatient assessment. The intervention will include electronic health record integration. We will design implementation processes for this program using the integrated Promoting Action on Research Implementation in Health Services (i-PARIHS) framework, adapted for the VA QUERI. We will design 3 phases of implementation: 1) implementation intervention planning through workflow analysis, technology assessments, and recipient/stakeholder interviews; 2) formative evaluation of pilot implementation at two vanguard sites to test initial acceptability and equipment performance; and 3) implementation fidelity monitoring by assessing consistency and satisfaction.

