## 5.0 Study Procedures

### 1). Experimental Procedures

**Participant Identification:** We will identify patients for inclusion in the study during hospitalization at the VA hospital prior to discharge or during routine clinic visits at the Heart Failure/Cardiology Clinic. The principal investigator ([name]) or the research coordinator ([name]) or the co-investigator will approach the patients in the hospital during their

stay or at the Heart Failure/Cardiology Clinic to discuss participation in this study. Charts will be screened at study locations for diagnosis of heart failure. Patients with such diagnosis will be approached in person by the aforementioned study team members and told about the study. If the patient is interested, further review will be completed with them all in a confidential manner.

**Participant Recruitment and Training:** All patients admitted to VA Medical Center in Salt Lake City with heart failure or seen in the Heart Failure Clinic or General Cardiology Clinic, who meet eligibility criteria, will be screened by a research coordinator, PI and Co-investigators. Patients meeting eligibility criteria will be approached regarding participation in this study. The PI and the other sub-investigators will be responsible for the care of these patients when they get admitted to the hospital or seen in the clinic. The PI, the Co-investigators and study coordinators will invite the potential participants into the study (if they meet inclusion/exclusion criteria) and explain to them the procedure in detail. If the patients agree to participate in the study, they will be asked to sign the consent form. We are not planning to post flyers or send recruitment letters. Follow-up phone calls will be made within one week to one month after enrollment.

After consenting, all subjects will be trained on placement of the device on the skin with supervision, guidance, and directions from the study team. The subject will have ample time to try the device themselves as the site will have extra adhesives and inactive devices for the purposes of demonstration. Subjects may be trained and fitted as hospital in-patients and re-trained in clinic when necessary. Written take-home instructions will also be provided.

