### **Study Discontinuation**

Insufficient or poor-quality data

If subjects opt not to wear the device, or if the telemonitoring data are of poor quality, the study team may decide to discontinue the subject from the study.

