### **Definition of Medical Events**

Primary Events

1. The proportion of randomized patients who meet the algorithm's criteria for at least one alert;
2. The ratio of the number of days the remote monitor is functioning properly (patient wearing device and data quality sufficient to make the daily decision) to the total number of days in the study;
3. The rate of HF hospitalization, all-cause hospitalization and LOS for those hospitalized;

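### The plan permits, without limit on content or recipients, release of by-arm interim data to investigators once the DSMB deems any protocol modification necessary

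*Combined protocol and SAP*

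**What the plan says.** All references are to the combined protocol and SAP.

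- **Looks.** Section 6.0, Adverse Event and Serious Adverse Event: "Two interim analyses will be performed, once 50 subjects and 100 subjects complete the study". Their main purpose is patient safety.
- **Content.** The data coordinating center prepares the tables for the DSMB. Sensor-related events are shown for everyone. Adverse events related to "heart failure therapy will be tabulated by randomization assignment". The events listed under this category are over-diuresis, drug-induced hypotension, other events attributed to HF therapy, and hospitalization.
- **Release rule.** "The detailed data by randomization group will not be shared with study investigators unless a protocol modification is deemed necessary by the DSMB".
- **Overlap with outcomes.** Definition of Medical Events lists among the primary events: "The rate of HF hospitalization, all-cause hospitalization and LOS for those hospitalized". Section 5.6 plans by-arm proportions with an HF hospitalization and a risk ratio between arms.
- **Roles of the possible recipients.** Section 5.0 has the PI, co-investigators and coordinators inviting patients to join, and adds: "The PI and the other sub-investigators will be responsible for the care of these patients" when they are admitted or seen in clinic. When an acute care episode is found to be an exacerbation, "the site PI will make a determination of the timing and cause of the exacerbation". If the device is not worn or its data are poor, "the study team may decide to discontinue the subject from the study".
- **DSMB traffic.** The Data Monitoring section has the investigators, not the coordinating center, supplying data and summary reports to the DSMB. The DSMB's findings return to the site by letter. Nothing there says that by-arm results are left out in either direction.

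**The concern.** The plan treats the by-arm comparison as something investigators should not see, then lifts that protection on a broad trigger. A modification the DSMB thinks necessary may be minor and may have nothing to do with the comparison, yet the clause applies all the same. It does not say which tables may be released or to which investigators, and it names no intermediary. Section 8.0 has changes to study procedures discussed on calls with input from all the PIs, so what one investigator learns could reach every site.

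Someone who knows the interim trend may, without intending it, recruit differently, discontinue a poorly adherent subject more or less readily, or judge the cause of an admission differently by arm. The estimates exposed are the by-arm hospitalization proportions and the risk ratio, which are meant to inform a pivotal trial with HF hospitalization as its primary outcome. Any modification drafted with the tables in hand would also be shaped by the comparison. Release cannot be undone.

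**Working it through.** **1. The plan's own figures.** Section 5.6 justifies the sample size by precision, and its figures reproduce:

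- Alert proportion, 240 subjects: 1.96 × √(0.25/240) = 0.063.
- Alert proportion, 180 subjects: 1.96 × √(0.25/180) = 0.073.
- Device-time ratio, SD 0.289, 180 subjects: 1.96 × 0.289/√180 = 0.042.

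None of these is a comparison between arms, so none depends on who sees interim tables. The plan states no alpha, power or stopping boundary.

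**2. How much of the study follows each look.** Section 3.0: "We plan to enroll and randomize 240 subjects".

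- First look: (240 − 50)/240 = 190/240 = 79% have not completed.
- Second look: (240 − 100)/240 = 140/240 = 58% have not completed.

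Some of these patients are already enrolled at the look, and the documents do not say how many. Enrollment bias cannot touch those patients, but their remaining follow-up and event judgements can still be affected.

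**3. How misleading a released table could be.** With 1:1 allocation, the looks hold about 25 and 50 completers per arm. The documents give no hospitalization rate, so I assume 25% in both arms, with a range of 15% to 30%. With X and Y independent binomial (n, p), the chance of an observed gap of at least 10 points is P(|X − Y| ≥ k). At n = 25, 10 points is 2.5 events, so k = 3. At n = 50, k = 5.

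| Completers per arm | p = 15% | p = 25% | p = 30% |
|---|---|---|---|
| 25 | 32% | 41% | 44% |
| 50 | 21% | 30% | 33% |

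These are exact binomial values. The normal approximation, with SE = √(2p(1 − p)/n), gives SE 0.122 and 41% at n = 25 and p = 25%, but SE 0.087 and only 25% at n = 50. It understates the second figure because the difference is discrete.

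**4. Precision of the comparison.** The 95% half-width of the risk difference is 1.96 × SE. At p = 25% this is 1.96 × 0.122 = 0.24 at the first look and 1.96 × 0.087 = 0.17 at the second.

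**5. Does another section narrow the clause?** I found none that does. The Data Monitoring section gives a second account of who prepares DSMB material and sets no restriction on the letters to the site.

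These figures describe how noisy a released table would be. They do not estimate the probability of release or the size of any resulting bias; the documents give no basis for either.

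**The case against.** **The clause does not order release.** A reader might infer that by-arm data go to investigators whenever the DSMB asks for a change. The text does not say that. It sets a default of withholding and lifts it when a modification is deemed necessary. Harm needs three steps: a necessary modification, actual sharing, and a reaction. This objection stands and limits the weight of the point. What remains is a permission with no bounds.

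**This is a feasibility study.** A reader might infer inflated type I error or a threat to the main feasibility results. The documents support neither. No hypothesis test governs the design, alerts come from an algorithm, and device time is read from the monitor. This stands, but the by-arm hospitalization estimates in section 5.6 are planned outputs and remain exposed.

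**Investigators may not treat or classify.** Section 5.0 gives the PI and sub-investigators responsibility for care, but also leaves treatment decisions to the clinical care team and says the research team does not answer alerts. The listed safety events are to be adjudicated, by whom is not stated, and counting all-cause admissions needs no judgement of cause. So the treatment and classification routes are only partly supported. Enrollment, discontinuation, and the site investigator's ruling on timing and cause remain.

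**Assignment may already be known.** Alerts reach clinicians in one arm only. That is true, but knowing one patient's arm is different from knowing the pooled trend, and the plan itself treats the trend as worth withholding. How much the trend adds cannot be quantified from the documents.

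**Conclusion.** The concern holds as an unlimited permission. Once the DSMB deems any modification necessary, nothing in the plan stops detailed by-arm tables from reaching people who enroll patients, may discontinue them and judge exacerbations. That could bias the by-arm hospitalization proportions and risk ratio. It leaves the alert proportion and device-time ratio largely untouched.

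The scale is conditional on release. Up to 79% of patients at the first look and 58% at the second would complete afterwards. The table shown could easily mislead, with about a 41% and then a 30% chance of a spurious gap of 10 points or more. This rests on the assumed 25% event rate, equal arms and no true difference. It also rests on reading the hospitalization entry as part of the by-arm tables, which is where the plan places it; the plan does not say whether that entry means all admissions or only those attributed to therapy.

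The change should be made because it costs almost nothing and is of little use after a release. The documents do not show that a release is likely.

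**What to change.** 1. **Rewrite the release sentence in section 6.0.** The DSMB sends investigators its recommended modification and the safety reason, without by-arm data. If figures are essential, they go only to a sponsor official who does not enroll, treat or classify patients, and the release is documented.
2. **Align the Data Monitoring section.** By-arm reports come from the data coordinating center rather than the investigators, and DSMB letters to the site omit by-arm results. Without this step a second route stays open.
3. **Name the adjudicator** of the listed events and state how that role relates to the site investigator's determination of timing and cause.

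The cost is a few sentences, with no change to sample size, visits or patient care. The downside is that investigators would draft any modification from the DSMB's stated reason rather than from the tables.
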